**Other:**

- Subjects non-compliant with study treatment.

**3.4. Individual Stopping Rules for Psoriasis Subjects**

**Treatment with PF-06826647 will be discontinued and the subject withdrawn from this study for:**

**Adverse Events:**

- Serious infections, defined as any infection (viral, bacterial, and fungal) requiring parenteral antimicrobial therapy or hospitalization.
- Other treatment emergent serious or severe AEs, after consultation with the Pfizer clinician.

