### 3.1.2. Psoriasis Multiple Dose Cohorts

In the multiple dose psoriasis subject cohorts, approximately 42 subjects will be enrolled with approximately 14 subjects receiving placebo, and approximately 28 subjects receiving one of two possible PF-06826647 dose levels, for 28 days. PF-06826647 dose range for the psoriasis cohorts will be selected based on emerging PK, CCI and safety data from the healthy subjects SAD/MAD periods. Refer to Protocol Section 1.3.4.1 for psoriasis dose selection rationale. QD dosing is planned for psoriasis subjects, however, daily dosing regimen (eg, QD, BID) may be adjusted based on emerging PK data from the SAD/MAD periods. Psoriasis subjects who discontinue early from the trial may be replaced at the discretion of the sponsor. PF-06826647 dose level in psoriasis may be adjusted based on emerging clinical data from the planned interim analysis, at the discretion of the Sponsor. Any potential PF-06826647 dose adjustments for psoriasis Cohort 2 will be applied after review of PK, CC and safety data up to 28 day in the 400 mg psoriasis cohort.

Initiation of dosing in psoriasis subjects will be based on available safety data from the healthy subject MAD period. Psoriasis subjects enrolled into the multiple dosing period will receive PF-06826647 or placebo (QD) for 28 days, with a 56 day follow-up period post last dose. Doses will be selected based on emerging PK, PD and safety data from the study (not to exceed  $C_{max}$  and  $AUC_{0-24}$  limits of 1870 ng/mL and 16,600 ng·h/mL, respectively). Dosing in psoriasis subjects will commence if adequate safety is demonstrated in healthy subjects participating in the MAD period at the equivalent dose level. At a minimum, 10 day safety and PK data from at least 6 healthy subjects (with at least one subject on placebo) receiving the equivalent QD dose level will be reviewed to confirm that a given PF-06826647 dose is safe and well tolerated before administering PF-06826647 to psoriasis subjects. Subjects will be housed through Day 28 of the multiple dosing period, discharged on Day 28, to return for outpatient visits on the mornings of Days 35 ( $\pm 3$  days), 42 ( $\pm 3$  days), 56 ( $\pm 3$  days) and 84 ( $\pm 3$  days)(end of study). The 28 day treatment duration is supported by preclinical toxicology data and will facilitate assessment of CCI, as well as assessment of clinical endpoints (eg, PASI).

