#### **6.4. Subject Withdrawal/Early Termination**

Subjects may withdraw from the study at any time at their own request, or they may be withdrawn at any time at the discretion of the investigator or sponsor for safety (see also the [Withdrawal From the Study Due to Adverse Events](#) section) or behavioral reasons, or the inability of the subject to comply with the protocol-required schedule of study visits or procedures at a given investigator site. The early termination visit applies only to subjects who are randomized and then are prematurely withdrawn from the study.

It may be appropriate for the subject to return to the clinic for final safety assessments to be scheduled as early as practically feasible following the decision to withdraw from the study. Subjects should be questioned regarding their reason for withdrawal. At the early withdrawal visit, every effort must be made to complete the following assessments:

- Physical examination;
- Supine blood pressure and pulse rate measurements and oral temperature;
- 12-lead ECG measurement;
- Blood and urine specimens for safety laboratory;
- Blood sample for pharmacokinetic analysis \*.

\* For subjects who discontinue early during the treatment period due to an adverse event, a final PK sample should be collected when possible. Subjects discontinuing early for other reasons may not be asked to provide a final PK sample, depending on when in the study discontinuation occurs. For such cases, please contact the study sponsor for further guidance.

Lack of completion of all or any of the early termination procedures will not be viewed as protocol deviations so long as the subject's safety was preserved.

Subjects who withdraw from the study may be replaced at the discretion of the investigator upon consultation with the sponsor (provided the nature of the safety event does not preclude dose escalation and exposure stopping limits are observed).

Replacement of psoriasis subject(s) who discontinue early may occur at discretion of the sponsor in order to ensure adequate number of subjects completing through Day 28.

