**Withdrawal of consent:**

Subjects who request to discontinue receipt of study treatment will remain in the study and must continue to be followed for protocol-specified follow-up procedures. The only exception to this is when a subject specifically withdraws consent for any further contact with him or her or persons previously authorized by the subject to provide this information. Subjects should notify the investigator in writing of the decision to withdraw consent from future follow-up, whenever possible. The withdrawal of consent should be explained in detail in the medical records by the investigator, as to whether the withdrawal is only from further receipt of investigational product or also from study procedures and/or posttreatment study follow-up, and entered on the appropriate case report form (CRF) page. In the event that vital status (whether the subject is alive or dead) is being measured, publicly available information should be used to determine vital status only as appropriately directed in accordance with local law.

If the subject withdraws from the study and also withdraws consent for disclosure of future information, no further evaluations should be performed and no additional data should be collected. The sponsor may retain and continue to use any data collected before such withdrawal of consent.

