#### **8.1.4. Time Period for Collecting AE/SAE Information**

The time period for actively eliciting and collecting AEs and SAEs (“active collection period”) for each subject begins from the time the subject provides informed consent, which is obtained before the subject’s participation in the study (ie, before undergoing any study-related procedure and/or receiving investigational product), through and including a minimum of 28 calendar days; except as indicated below after the last administration of the investigational product.

For subjects who are screen failures, the active collection period ends when screen failure status is determined.

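### Protocol 3.4 takes psoriasis subjects who meet most stopping rules out of the study as well as off treatment, which loses the scheduled follow-up visits and, for an early stop, the Day 28 PASI

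*Protocol*

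**What the plan says.** Protocol Section 3.4 (Individual Stopping Rules for Psoriasis Subjects) is headed "Treatment with PF-06826647 will be discontinued and the subject withdrawn from this study for". Under that heading come serious infections, other serious or severe adverse events (after consultation with the sponsor's clinician), a table of laboratory limits, ECG limits, blood pressure rises and non-compliance. The blood pressure paragraph is worded differently: it says that dosing should stop and the pressure be followed, and does not mention leaving the study.

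Section 6.4, under Withdrawal of consent, treats the voluntary case the other way: "Subjects who request to discontinue receipt of study treatment will remain in the study and must continue to be followed for protocol-specified follow-up procedures". The one exception is refusal of any further contact.

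For a subject who is withdrawn, Section 6.4 foresees "final safety assessments to be scheduled as early as practically feasible following the decision to withdraw from the study". The assessments listed are physical examination, vital signs, ECG, safety laboratory samples and a PK sample; PASI is not named. The section adds that "Lack of completion of all or any of the early termination procedures will not be viewed as protocol deviations", provided that safety was preserved. It also says "Replacement of psoriasis subject(s) who discontinue early may occur at discretion of the sponsor".

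Section 3.1.2 plans 28 days of dosing "with a 56 day follow-up period post last dose". Subjects are housed during dosing and "discharged on Day 28, to return for outpatient visits on the mornings of Days 35", 42, 56 and 84. SAP Section 9.3 defines Week 4 as Days 25 to 31.

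Some follow-up survives withdrawal. Section 3.5 follows any subject who meets discontinuation criteria every 1 to 2 weeks, with retesting, until the event is normal, at baseline or stable. Section 8.1.4 collects adverse events "through and including a minimum of 28 calendar days" after the last dose, and Section 6.3.1 adds a contact at 28 to 35 days, which may be by telephone.

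**The concern.** Safety is the primary objective in the psoriasis cohorts, and most of the rules in Section 3.4 are safety rules. As written, the subjects who show a signal leave the visit schedule, while those who stop for their own reasons stay on it. Unscheduled retesting of the known abnormality is not the same as scheduled visits that look for something new.

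The second stake is the Day 28 PASI, a secondary endpoint that Protocol Section 9.7 uses at the interim on the 400 mg cohort to inform the dose of the next cohort. If a subject is stopped because of a drug effect, the missing Day 28 value may be related to treatment, and the repeated measures model then has to treat it as missing at random. Several stop parameters (lymphocytes, white cells, hemoglobin, ALT and AST) are ones that the drug moved in animals according to Protocol Section 1.2.4, although those changes were judged not adverse.

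**Working it through.** **1. What a rule-based stop loses.** Take a stop at Day 14.

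| Item | Subject stopped by rule (3.4) | Subject who chooses to stop (6.4) |
|---|---|---|
| Triggering event | followed every 1 to 2 weeks until stable (3.5) | followed if an adverse event is open |
| Minimum adverse event collection | Day 14 + 28 = Day 42 | Day 14 + 28 = Day 42 |
| Withdrawal visit | as soon as feasible; not enforced | not needed |
| Week 4 PASI (Days 25 to 31) | none required | stays on schedule |
| Visits at Days 35, 42, 56, 84 | none required | stay on schedule |

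The 28-day minimum is the same in both columns, and also for a completer (Day 28 + 28 = Day 56), so it is not part of the loss. The loss is the last two rows. A PASI taken at a prompt withdrawal visit near Day 14 would fall in the Week 2 window (Days 11 to 17) and could not serve as a Day 28 value. Day 84 appears lighter on safety: the vital signs footnote to the psoriasis schedule names follow-up measurements at Days 29, 35, 42 and 56/ET, but not Day 84.

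**2. The plan's own figure.** Inputs from Protocol Section 9.1.2: difference -7.8, SD 8, 14 per arm, one-sided alpha 5%. A two-sample t-test with 26 degrees of freedom and noncentrality 7.8 / (8 × √(2/14)) = 2.58 gives 80.69% power, which matches the stated 80.7%. The inputs can therefore be used below.

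**3. How many stops?** The documents give no rate. Section 1.3.2 reports that the stopping criteria of Section 3.3 had not been met with 53 healthy subjects treated with drug or placebo. The psoriasis limits are tighter (lymphocytes below 800 rather than 500 per mm³; ALT or AST above 2.5 rather than 5 times the upper limit; an added white cell limit of 3000 per mm³), and dosing lasts 28 days rather than 10. I assume k = 1 to 3 of 14 active subjects, with 3 as the extreme.

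**4. Gap between the all-treated and on-drug PASI effect.** Gap = 7.8 × (1 − share of effect kept at Day 28) × k/14. Within-cohort standard error (14 active, 7 placebo) = 8 × √(1/14 + 1/7) = 3.70.

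| k | Half kept | None kept | Gap / SE |
|---|---|---|---|
| 1 | 0.28 | 0.56 | 0.08 to 0.15 |
| 2 | 0.56 | 1.11 | 0.15 to 0.30 |
| 3 | 0.84 | 1.67 | 0.23 to 0.45 |

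**5. Precision without replacement.** If the stoppers' earlier values are ignored, SE = 8 × √(1/(14 − k) + 1/7) = 3.75, 3.81 (3.805 before rounding) and 3.87 for k = 1, 2, 3, a rise of 1.3%, 2.7% and 4.4%. The planned model does use earlier values. With four weekly visits, stoppers seen at Weeks 1 and 2 only, SD 8 at each visit and an assumed equal correlation of 0.6, the SE is 3.73, 3.76 and 3.80.

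**The case against.** The strongest reply is that safety follow-up is already handled. Section 3.5 comes directly after the stopping rules and covers every subject who meets them; while the event is open, follow-up every 1 to 2 weeks is at least as dense as visits at Days 35, 42, 56 and 84. This stands. A reader might infer that subjects stopped for safety are dropped from observation, and the documents do not support that. Nor do they support the idea that Section 3.4 halves follow-up from 56 to 28 days: the 28-day adverse event minimum in Section 8.1.4 applies to everyone. What Section 3.5 does not do is require visits once the triggering event has settled, and it names no PASI.

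A reader might also infer that the planned PASI estimate is biased. Protocol Section 9.2 keeps subjects with a baseline and any post-baseline value, and Section 9.2.1 fits a repeated measures model, so stoppers still contribute. The gaps in the working are between two target effects. Even the extreme of 1.67 points lies well inside the interim 90% confidence interval, whose half-width is about 1.73 × 3.70 = 6.4 points. The SAP plans no hypothesis test or decision rule (Sections 4.1 and 4.2), and replacement can restore the number of completers, though not the outcomes of those who stopped.

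Two further limits are fair. Not every rule clearly leads to withdrawal, given the blood pressure wording. And part of the text is not available for review: the PASI row and some footnotes of the psoriasis schedule, and SAP Section 8.2.2.1. An early termination PASI may therefore exist (photography is listed at Day 56/Early Termination), but well before Day 25 it would not be a Day 28 value.

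Finally, withdrawing a subject after a safety trigger is a permitted choice in Phase 1, and Section 6.4 allows it. That is true, but the protection comes from stopping the drug, which the fix leaves in place.

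**Conclusion.** The point holds in a limited form. Section 3.4 ties treatment discontinuation to study withdrawal for the adverse event, laboratory, ECG and non-compliance rules, and is unclear for blood pressure. No available text keeps these subjects on the scheduled visits at Days 35, 42, 56 and 84 or, after a stop well before Day 25, on the Day 28 PASI. The loss is scheduled surveillance for new events plus one efficacy value per early stopper.

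The size is small, and zero if nobody stops: a 0.3 to 1.7 point difference between target effects (0.08 to 0.45 of a standard error of 3.70), and a rise in standard error of about 1% to 4% at most. These figures rest on an assumed 1 to 3 active stoppers of 14 who keep half or none of a 7.8-point effect; the documents supply neither assumption. The reason to act is that the primary objective is safety and the change is cheap.

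**What to change.** In Section 3.4, make the consequence of meeting a rule discontinuation of treatment only, and use the same wording for blood pressure. Leave all thresholds unchanged. State that, unless consent is withdrawn, the subject keeps the Day 28 PASI and the scheduled follow-up visits through Day 84. In the SAP, use off-drug PASI values only in a sensitivity analysis beside the on-treatment repeated measures estimate, unless Section 8.2.2.1 already settles their use.

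The cost is one wording change, possibly one SAP sentence, and for each early stopper either one added Day 28 visit or a continued stay in the unit; the later visits are already in the schedule. The drawback is that off-drug PASI values, perhaps taken after other psoriasis treatment, need separate interpretation. The on-treatment estimate itself would still rest on missing at random; the sensitivity analysis would show how much that matters.

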**Laboratory, Vital Sign, and ECG Abnormalities:**

Individual stopping rules below will be based on repeated measures (single repeat preferably performed within 24 hours of initial result) of the parameters outlined below.

Laboratory Variable	Laboratory Value
Hematology	
Absolute Neutrophil Count	<1000/mm  ; <1.0 x10  /L
Hemoglobin	<10.0 g/dL; <6.2 mmol/L; <100 g/L
Platelet count	<75,000/mm  ; <75.0x0x10  /L
WBC	<3000/mm  ; <3.0x10  /L
Lymphocytes	<800/mm  ; <0.8x10  /L
Chemistry	
AST	>2.5x ULN
ALT	>2.5x ULN
Creatinine (serum)	>1.5x ULN
Total bilirubin a	>1.5x ULN

a Total bilirubin  $\geq 1.5$  x ULN; subjects with a history of Gilbert's syndrome may have a direct bilirubin measured and would be eligible for this study provided the direct bilirubin is  $\leq$  ULN.

- Changes in liver function tests that meet Hy's Law criteria.

**Note:** An increase of  $\geq 0.3$  mg/dL (or  $\geq 26.5$   $\mu$ mol/L) in serum creatinine relative to subjects' own baseline measurement should trigger another assessment of SCr within 24-hours from awareness. See [Potential Cases of Acute Kidney Injury](#) for further guidance.

- 12-lead ECG demonstrating QTc  $\geq 500$ ; or a QRS interval  $\geq 140$  msec or  $\geq 50\%$  increase from baseline; PR interval  $\geq 300$  msec or 25% increase over baseline when baseline  $> 200$  msec.

Blood pressure measurements meeting criteria for individual stopping rules should be repeated at least twice, separated by at least 5 minutes, with the subject at rest, supine. If confirmed to be abnormal, and confirmed to be clinically significant by investigator, dosing should be stopped and the blood pressure should be followed periodically, as deemed appropriate by the investigator, until the blood pressure are returned to within normal limits or deemed acceptable by the investigator.

- Diastolic: recurrent or persistent ( $\geq 24$  hrs) or symptomatic increase from baseline, in same posture, by  $> 20$  mmHg.
- Systolic: recurrent or persistent ( $\geq 24$  hrs) or symptomatic increase from baseline, in same posture, by  $> 30$  mm Hg.

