Vital signs: Supine single PR, BP and Oral Temperature i	X	X		X	X	X	X		X		X	X	X	X	X		X	X	X	X	X	X	X	X	X	X	X	X	X	X	X	X	X	
24 hr Urine Collection for CCI measurement, Creatinine Clearance, 6-β-Hydroxycortisol/cortisol ratio and Urine PK j	0-24 hr									0-24 hr																								
Study Treatment Administration		X									X	X	X	X	X		X																	
PK Blood Sampling k		X	X	X	X	X	X	X			X		X		X		X	X	X	X	X	X	X	X	X	X	X	X	X	X	X			
CCI																																		
Serious and non-serious adverse event monitoring	X	X									→	→	→	→	→		→	→	→	→	→	→	→	→	→	→	→	→	→	→	→	→	X	
Prior/Concomitant treatment	X	→									→	→	→	→	→		→									→	→	→	→	→	→			
CCI																																		

Abbreviations: →= ongoing/continuous event; BP = blood pressure; CCI [redacted]; CRU = clinical research unit; CCI [redacted]; ECG = electrocardiogram; CCI [redacted]; PK = Pharmacokinetics; PR = pulse rate; CCI [redacted]

- a. End of study procedures ( $\pm 3$  day).
- b. Prior to dosing on Day 1, confirm that safety labs, ECG, and vital sign results, contraception check and prior/concomitant treatments from Day -1 (or from Day 8 of SAD if obtained within 48 hours of MAD Day -1) meet eligibility requirements outlined in [Section 4.2](#). If labs, vitals, or ECG results are not within limits as outlined in [Section 4.2](#), the site will notify sponsor. PI and sponsor will make the determination as to whether or not to allow the subject to continue into the MAD period. If the out of range values meet individual stopping rules outlined in the protocol, the subject will not continue into the MAD period.
- c. See protocol [Section 4.6.4](#) (Contraception). Investigator will discuss appropriate contraception methods with male subjects.
- d. Subjects will reside in the clinical research unit until the morning of Day 14, returning on the morning of Day 28  $\pm 3$  days for the end of study procedures visit.
- e. Limited physical examination (at the discretion of the principle investigator, exam may be limited or full).
- f. Chemistry and hematology labs are collected following fasting period of at least 8 hours (on Day 10, fasting applies to hour 0 labs only).
- g. Lipid panel (Cholesterol, Triglycerides, HDL, and LDLc): Fasting requirement of at least 8 hours.
- h. ECGs will be collected in triplicate approximately 2-4 minutes apart on Days 1, 2, 4, 6, 8, 10 and Day 11. Single ECGs will be collected at all other specified visits.

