#### **4.4. Exclusion Criteria: Psoriasis Multiple Dose Cohort**

Subjects presenting with any of the following characteristics/conditions will not be included in the study:

1. Currently have non-plaque forms of psoriasis, eg, erythrodermic, guttate, or pustular psoriasis.
2. Have current drug-induced psoriasis, eg, a new onset of psoriasis or an exacerbation of psoriasis from beta blockers, calcium channel blockers, antimalarial drugs or lithium.
3. If planned initiation of, or changes to, concomitant medication that could affect psoriasis (eg, beta blockers, calcium channel blockers, antimalarial drugs or lithium) are to occur within 2 weeks prior to randomization and/or during the study.
4. Subjects with ANY of the following abnormalities in clinical laboratory tests at screening, as assessed by the study-specific laboratory and confirmed by a single repeat, if deemed necessary:
  - a. Hemoglobin:
    - If the hemoglobin level is greater than 5% below the lower limit of normal (LLN), subject is to be excluded;

- If the hemoglobin level is within 5% below the LLN, iron and folate levels are to be measured: if iron and/or folate levels are below the LLN, subject is to be excluded.
  - b. Absolute neutrophil count of  $<2 \times 10^9/L$  ( $<2000/mm^3$ ).
  - c. Platelet count below the LLN.
  - d. Serum creatinine level above the upper limit of normal or an estimated Glomerular Filtration Rate (GFR) value  $\leq 80$  mL/min, based on the Cockcroft-Gault calculation, at Screening (see [Appendix 2](#)).
  - e. Aspartate aminotransferase (AST)/serum glutamic oxaloacetic transaminase (SGOT) or alanine aminotransferase (ALT)/serum glutamic pyruvic transaminase (SGPT)  $\geq$  values more than 1.5 times the upper limit of normal.
  - f. Fasting glucose  $>140$  mg/dL.
  - g. Total bilirubin  $\geq 1.5 \times$  ULN; subjects with a history of Gilbert's syndrome may have a direct bilirubin measured and would be eligible for this study provided the direct bilirubin is  $\leq$ ULN.
5. Any psychiatric condition including recent or active suicidal ideation or behavior that meets any of the following criteria:
- Suicidal ideation associated with actual intent and a method or plan in the past year: “Yes” answers on items 4 or 5 of the Columbia suicide severity rating scale (C-SSRS) ([Appendix 9](#)).

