  - Previous history of suicidal behaviors in the past 5 years: “Yes” answer (for events that occurred in the past 5 years) to any of the suicidal behavior items of the C-SSRS.
  - Any lifetime history of serious or recurrent suicidal behavior.
  - Suicidal behaviors questionnaire –revised (SBQ-R) ([Appendix 10](#)) total score  $\geq 8$ .
  - Clinically significant depression: patient health questionnaire – 8 items (PHQ-8) ([Appendix 11](#)) when the total score  $\geq 15$ .
  - The presence of any current major psychiatric disorder that is not explicitly permitted in the inclusion/exclusion criteria.
  - In the opinion of the investigator or Pfizer (or designee) exclusion is required.

6. Have current or recent history of severe, progressive, or uncontrolled renal, hepatic, hematological, gastrointestinal, metabolic, endocrine, pulmonary, cardiac, neurological or allergic disease (including drug allergies, but excluding untreated, asymptomatic, seasonal allergies at time of dosing).
7. Will have vaccination with live virus, attenuated live virus, or any live viral components within the 6 weeks prior to the first dose of study drug or is to receive these vaccines at any time during treatment or within 8 weeks following completion of study treatment.
8. Will have routine household contact with individuals who have received vaccination with live virus, or attenuated live virus, for 8 weeks following completion of study treatment.
9. Have a history of any lymphoproliferative disorder (such as Epstein Barr Virus [EBV]-related lymphoproliferative disorder, as reported in some subjects on other immunosuppressive drugs), history of lymphoma, leukemia, myeloproliferative disorders, multiple myeloma, or signs and symptoms suggestive of current lymphatic disease.
10. Have a clinically significant infection currently or within 6 months of first dose of study drug (eg, those requiring hospitalization or parenteral antimicrobial therapy or opportunistic infections), or a history of chronic or recurrent infectious disease.
11. Have or have had symptomatic herpes zoster or herpes simplex within 12 weeks, more than one episode of local herpes zoster, or a history (single episode) of disseminated zoster.
12. Any prior treatment with lymphocyte depleting agents/therapies (such as CamPath® [alemtuzab], alkylating agents [eg, cyclophosphamide or chlorambucil], total lymphoid irradiation, etc).

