27. Other acute or chronic medical or psychiatric condition including recent (within the past year) or active suicidal ideation or behavior or laboratory abnormality that may increase the risk associated with study participation or investigational product administration or may interfere with the interpretation of study results and, in the judgment of the investigator, would make the subject inappropriate for entry into this study.

28. Have any other condition which would make the subject unsuitable for inclusion in the study.
29. Subjects who are investigator site staff members directly involved in the conduct of the study and their family members, site staff members otherwise supervised by the investigator, or subjects who are Pfizer employees, including their family members, directly involved in the conduct of the study.
30. Pregnant female subjects; breastfeeding female subjects; female subjects of childbearing potential.
31. Fertile males subjects who are unwilling or unable to use a highly effective method of contraception as outlined in this protocol for the duration of the study and for at least 28 days after the last dose of investigational product.
32. Use of tobacco/nicotine containing products in excess of  $\geq 5$  cigarettes/day.
33. A positive urine drug screen.
34. Consumption of grapefruit or grapefruit juice or citrus fruits eg, Seville oranges, pomelos within 7 days prior to the first dose of study medication until collection of the final pharmacokinetic blood sample.
35. Require treatment with prohibited concomitant medication(s) listed in [Appendix 3](#) or have received a prohibited concomitant medication in the 4 weeks prior to the first dose of study drug. Subjects receiving non-prohibited concomitant medications for any reason must be on a stable regimen, which is defined as not starting a new drug or changing dosage within 2 weeks or 5 half-lives (whichever is longer) prior to first dose of study drug.
36. Have previously been treated with efalizumab (Raptiva®).
37. Have previously been treated with secukinumab (Cosentyx) or ixekizumab (Taltz).
38. Have previously been treated with ustekinumab (Stelara®).
39. Have received any of the following treatment regimens specified in the timeframes outlined below:

Biologic therapies for psoriasis (including brodalumab) have discontinuation periods determined from approximately 5x half-life of the respective biologic.

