#### **4.5. Randomization Criteria**

Subjects will be randomized into the study provided they have satisfied all subject eligibility criteria.

Healthy subjects will be randomized (once) into the SAD period, at which time, they will receive treatment assignment (active PF-06826647 dose level or placebo) for both the SAD and MAD periods. Subjects will receive the same blinded treatment assignment (ie, the same

dose level of active PF-06826647 or placebo) throughout in both the SAD (Period 1) and MAD (Period 2) periods. Optional BID cohort subjects may be directly randomized to the twice daily 10 day treatment regimen once confirmation of eligibility criteria occurs, without the need to participate in a single dose period.

- The randomization ratio for the cohorts in the healthy subject SAD/MAD segment will be 3: 1 (PF-06826647:Placebo).
- The randomization ratio for the planned psoriasis multiple dose cohorts will be 2:1 (PF-06826647:Placebo).

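### Psoriasis exclusion 4 has no lymphocyte entry limit, although Section 3.4 mandates withdrawal on a repeated count below 800/mm3 whatever the baseline

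*Protocol*

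**What the plan says.** Protocol Section 3.4 introduces the psoriasis stopping list with "Treatment with PF-06826647 will be discontinued and the subject withdrawn from this study for". Its laboratory table has nine limits, one of them a lymphocyte count below 800/mm3. On confirmation it says "Individual stopping rules below will be based on repeated measures", meaning one repeat, preferably within 24 hours. The lymphocyte row does not mention baseline. The creatinine note and the blood-pressure limits in the same section do.

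Entry is governed by Section 4.4. Exclusion 4 covers "Subjects with ANY of the following abnormalities in clinical laboratory tests at screening, as assessed by the study-specific laboratory", and its items a to g are hemoglobin, neutrophils, platelets, creatinine or GFR, AST/ALT, fasting glucose and total bilirubin. Lymphocytes are not among them, and the list shows no redaction. Section 4.5 then says "Subjects will be randomized into the study provided they have satisfied all subject eligibility criteria", with no reference to Section 3.4.

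Three other exclusions touch the point without setting a count. Exclusion 12 bars "Any prior treatment with lymphocyte depleting agents/therapies". Exclusion 27 covers, in the investigator's judgment, a "laboratory abnormality that may increase the risk associated with study participation or investigational product administration or may interfere with the interpretation of study results". Exclusion 28 reads "Have any other condition which would make the subject unsuitable for inclusion in the study".

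**The concern.** A mandatory numeric stop normally has an entry limit on the safe side of it, so that nobody starts treatment already meeting the stop. Exclusion 4 follows that pattern for most of the Section 3.4 table but not for lymphocytes.

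What is at stake is first the subject. Someone whose count already requires withdrawal could have biopsies, be admitted and receive an investigational immunomodulator, only to be taken off it. Second is the reading of the withdrawal. Section 1.2.4 of the Protocol reports lower lymphocyte counts in rats and monkeys, so a stop that reflects a pre-existing count would look, at first sight, like the expected drug effect. Each psoriasis cohort has 14 active and 7 placebo subjects, so a single such case would draw attention.

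**Working it through.** The plan states no figure on this point, so the check sets entry limits against stops.

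| Parameter in 3.4 | Excluded at entry (4.4, exclusion 4) | Stop (3.4) |
|---|---|---|
| Neutrophils | <2000/mm3 | <1000/mm3 |
| Hemoglobin | more than 5% below LLN | <10.0 g/dL |
| Platelets | below LLN | <75,000/mm3 |
| AST | about 1.5x ULN | >2.5x ULN |
| ALT | about 1.5x ULN | >2.5x ULN |
| Creatinine | above ULN | >1.5x ULN |
| Total bilirubin | >=1.5x ULN | >1.5x ULN |
| WBC | none | <3000/mm3 |
| Lymphocytes | none | <800/mm3 |

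**Count.** Nine stops, two without an entry limit: 9 - 2 = 7 matched. For hemoglobin and platelets this assumes usual laboratory ranges, which the documents do not give. The hemoglobin entry limit lies above the stop if LLN exceeds 10/0.95 = 10.5 g/dL, and the platelet limit does so if LLN exceeds 75,000/mm3.

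**Can a subject pass entry and already be at the stop?** Take assumed counts of 2500 neutrophils, 700 lymphocytes and 400 other white cells per mm3. Total WBC = 2500 + 700 + 400 = 3600/mm3. With normal hemoglobin and platelets, this subject passes every hematology item in exclusion 4 and is clear of the WBC stop. A repeat of 700/mm3 meets the lymphocyte stop.

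**Is the WBC gap comparable?** No. With neutrophils at the entry floor of 2000 or above and lymphocytes at 800 or above, WBC below 3000 requires:
- neutrophils below 3000 - 800 = 2200/mm3, and
- all other white cells together below 3000 - 2000 - 800 = 200/mm3.

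Once lymphocytes have a limit, only that narrow corner remains.

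**Burden before the first dose.** Section 7.3 specifies two lesional and two non-lesional 4 mm biopsies on Day -1: 2 + 2 = 4.

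**Is the count already available?** Yes. Absolute lymphocytes are in the Table 7 hematology panel. Table 10 budgets 1 screening, 9 treatment-period and 3 follow-up safety draws: 13 x 14.5 mL = 188.5 mL, as the table states. The psoriasis schedule, as it can be read, marks both Screening and Day -1.

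**The case against.** **Eligibility is not only numeric.** Section 4 asks that all relevant conditions be weighed, and exclusions 27 and 28 would let an investigator refuse a subject whose count is already below a stop. Exclusions 6, 10, 12, 23 and 39 also shrink the pool. This stands as mitigation, but none of them names a count, and the plan did not leave neutrophils or platelets to judgment.

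**Part of the psoriasis schedule cannot be read.** Its first rows and footnotes a to e are missing from the public text, and a Day -1 check could be there. That is a real limit. Such a check would settle dosing. It would not necessarily spare the biopsies, which are taken on the same day, so a Screening limit still adds something.

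**Pre-dose values may already count.** Low results at Screening and on Day -1 could be read as the repeated measures in Section 3.4, so that no dose is given. The text does not exclude this. But Section 3.4 speaks of discontinuing treatment and Section 4.5 does not point to it, so the plan should say which reading applies. For the same reason, and because the 24-hour repeat is only preferred and result turnaround is not stated, no number of doses before a stop can be derived.

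**A reader might infer that healthy subjects already have this protection.** Footnote b of the MAD schedule says "If the out of range values meet individual stopping rules outlined in the protocol, the subject will not continue into the MAD period". It is triggered, however, by values outside the Section 4.2 limits, and Section 4.2 has no lymphocyte limit. It does not show an existing lymphocyte bar.

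**A reader might infer a biased safety result.** The documents do not support that. Each cohort has a placebo group, SAP 6.3.2 takes baseline laboratory status into account, and SAP 8.4.5 provides individual plots of change from baseline, where an unchanged low count would show. Under Protocol Section 6.4 the sponsor may replace the subject, which protects the number completing Day 28.

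**Conclusion.** The mismatch is real and can be verified in the text. The stop is mandatory and independent of baseline, the matching entry limit is absent, and only investigator judgment stands between a subject below 800/mm3 at Screening and the Day -1 biopsies and first dose. Of the nine laboratory stops, one (lymphocytes) has a practical entry gap and a second (WBC) a marginal one.

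No frequency is claimed, since the documents give no distribution of baseline lymphocytes in eligible subjects. Nor is any number of doses, directional bias or effect on the primary safety endpoint.

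The conclusion assumes that no unread psoriasis schedule footnote sets a lymphocyte limit at Screening. A footnote requiring only a Day -1 check would narrow the point to the Screening limit. This is a cheap improvement made for subject protection.

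**What to change.** 1. Add an item to exclusion 4 in Section 4.4: absolute lymphocyte count below 800/mm3, or a higher value chosen by the sponsor, confirmed by a single repeat if deemed necessary. Applied at Screening, this spares both the biopsies and the dosing.
2. State in Section 4.5 that Day -1 hematology must be clear of the Section 3.4 limits before the first dose. This catches a count that falls between Screening and Day -1, and it also covers the WBC corner. If a psoriasis schedule footnote already requires it, refer to that footnote.

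The cost is protocol wording and an occasional extra screen failure, in someone who would otherwise have to be withdrawn if the low count persisted. No new sample, visit or analysis is needed.
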